#### 1 ABSTRACT

Peyronie's disease (PD) is a fibrotic condition of the penis, affecting 1-13% of the US male population. The disease results in penile curvature and significant psychosocial bother. Current preferred therapies for PD include repeated penile injections with bacterial enzymes and surgery. However, these therapies are expensive and in some cases result in permanent reductions in penile length and sensation. Penile traction therapy (PTT) is a relatively newer treatment which has been proposed as a treatment for PD with preliminary data suggesting a potential role. However, currently available PTT devices are primarily designed for penile lengthening and have many significant limitations including a requirement of use for 9 hours daily and significant difficulties in personal application. Given these limitations, a new penile traction device (RestoreX®) was created and funded through Mayo Ventures and was specifically designed to treat men with PD. The primary objective of the current study is to evaluate safety of the device using various dosing schedules, with secondary endpoints designed to assess efficacy and subjective outcomes. To accomplish the study, a population of PD men will be enrolled and will be randomized to utilize the device for varying amounts of time. Outcomes will be periodically assessed, and results are to be used with the intent to publish in a scientific journal.

#### 2 SPECIFIC AIMS / HYPOTHESIS

## 2.1 Primary Objectives

1. Evaluate the safety of the RestoreX® device when used 30 minutes once daily, twice daily, three times daily, and in an open label fashion

## 2.2 Secondary Objectives

- 1. Compare changes in stretched penile length following completion of 3 months of RestoreX® therapy as well as following an open-label period within and among treatment groups.
- 2. Compare changes in penile curvature following completion of 3 months of RestoreX® therapy as well as following an open label period within and among treatment groups
- 3. Compare outcomes of subjective questionnaires assessing erectile function, PD diseasespecific domains, satisfaction, ability to achieve sexual intercourse, and pain among treatment groups
- 4. Compare satisfaction with the RestoreX® device to alternative forms of PTT among treatment groups
- 5. Compare satisfaction with the RestoreX® device to alternative PD therapies among treatment groups

The current study hypothesis is that deformities relating to PD (penile length loss, curvature) can be treated with penile traction therapy.

#### 3 BACKGROUND AND SIGNIFICANCE

Peyronie's disease (PD) is estimated to affect 1-13% of the male population and is associated with deposition of fibrous plaques within the tunica albuginea of the corporal bodies.[1-6] It is characterized by penile curvature, pain, shortening, impaired sexual function, and adverse effects on patient and partner well-being.[7, 8] While surgery remains the gold standard for the correction of penile curvature, multiple alternative treatment options including oral, intralesional injections, and mechanical vacuum or traction therapies are available, with variable success rates.[9, 10]

Penile traction therapy (PTT) consists of any treatment designed to lengthen or straighten the penis through mechanical forces. As a broad category, it also can include the use of vacuum erection devices (VED), which serve to expand the penis through application of hydrostatic forces, although the objective of the current study relates only to the more narrow definition of PTT.

Although various forms of PTT have likely been utilized to lengthen the penis for many years, the majority of data on its impact on penile length and curvature have only been reported recently. The increasing popularization of PTT as a treatment modality is likely secondary to several factors, including its relative non-invasive nature, adverse effects associated with alternative therapies, and the difficulty of treating conditions resulting in penile length loss. The scientific basis for use of traction therapy in general is well established, with mechanical stresses known to modulate multiple aspects of cellular function, including apoptosis, gene expression, and growth and differentiation.[11] In cases of fibrosis, such as with Dupuytren's contracture or Peyronie's disease (PD), continuous traction therapy has also been shown to reorient collagen fibrils and may have a differential effect on diseased versus non-diseased tissues.[12, 13]

PTT for the treatment of PD has been the subject of several studies.[14] While current evidence for PTT as monotherapy for PD is limited by small cohort sizes and low quality methodology, several studies have suggested significant improvements in stretched penile length (SPL), penile curvature (in acute phase of PD), and/or patient satisfaction.[15-17] PTT in conjunction with intralesional injections including verapamil and interferon has been assessed as well, with significant improvements found in SPL and no significant differences identified on penile curvature.[18-20]

#### 3.1 Limitations with Current PTT Devices

Currently available PTT devices have several notable limitations:

• The first and most important limitation is regarding regulatory approval. As a general class, orthotic-type devices intended to correct a deformity are considered Class I devices by the FDA. However, current devices are not designed to correct penile curvature, but are predominantly designed to lengthen the penis. As such, they fall outside of the Class I category and are therefore considered as novelty items with no claims as to role or efficacy. Only one PTT device (Andropenis®) has retroactively registered with the FDA as a 510k exempt Class II device (pending review by the FDA).

- A second limitation is that the devices are very difficult to use and often result in mild, temporary patient pain and discomfort. The clamping portion of the device alone often results in pinching of skin and transient pain with device application. In the largest (n=96) randomized controlled trial (RCT) performed of the device in men with PD, the authors noted penile erythema occurring in 2% and transient pain in 25%.[17]
- A third limitation is the duration of use required. Currently, the Andropenis® device is recommended to be used for 9 hours daily over a period of at least 3 months. This duration of use is clinically very challenging to achieve, and in our practice we have found that most patients are not able to utilize the device for over 1-2 hours daily.
- The Andropenis® device achieves very minimal traction on the penis. In assessments of patients utilizing the device, often no traction is achieved.
- Existing PTT devices do not have a mechanism by which curvature can be corrected. They are restricted to lengthening alone. They also are not allowed to make any claims specifically on lengthening in the US.
- With the exception of one device, existing PTT systems have not undergone clinical testing.

Given these numerous limitations, a novel PTT device has been developed at Mayo Clinic (Figure 1). The primary objective of the device was to assist in the treatment of PD, either as a primary or adjunctive therapy. The device addresses each of the above bullet points, and is designed to be a minimally-invasive alternative to existing treatments.

Figure 1 – RestoreX® device

## 3.2 Preliminary Data

Currently, there is a small amount of preliminary data available on the RestoreX® instrument. During the developmental phase of the device, a quality improvement project was performed to evaluate the clamping portion (see **Attachment – Quality Improvement Summary**). It was felt that the clamp represented the most critical aspect of the device, as this was where the majority of discomfort occurred with other devices. Additionally, the clamp needed to provide sufficient friction to allow adequate traction without having the glans of the penis dislodge from the device.

A total of 15 patients participated in the quality improvement project and had the clamps applied under direct supervision for 30 minutes. After the 30 minutes, all patients reported 0/10 pain, and only minimal transient erythema was documented by the physician. The clamp was again applied, and traction forces were administered to determine if the clamp was able to remain intact despite stretching forces applied. This also resulted in a successful outcome, with all patients able to successfully achieve a minimum required tension of 1 kg, with a 36% safety factor achieved before any discomfort was reported among any patient. During the testing, patients reported improved comfort with the use of a wrap such as gauze or Coban, which permitted additional traction in all patients.

## 3.3 Significance

The development of a novel PTT which addresses the above limitations is a significant milestone. As previously noted, no PTTs are currently designed to correct PD curvature, and only limited data are available on PTT use in this manner. In the absence of a more conservative therapy, the most common current first line treatment for PD is collagenase clostridium histolyticum (Xiaflex®). This therapy requires 10 physician visits over a 5 month period and costs >\$50,000 for a full treatment series. It also results in notable adverse events including risk of penile fracture and significant penile ecchymoses. The only other viable alternative is surgical management. This is associated with multiple undesirable adverse effects including penile shortening, penile edema, loss of penile sensation, and recurrence of curvature over time.

Traction therapy has been used in many applications including limb and dental orthotics (braces) with success for many years. It however has not been successfully applied in the case of chronic PD, as this has previously not been an area of legitimate scientific research and treatment. If the current study demonstrates the safety and efficacy of the current therapy on improving penile curvature, it has the possibility of displacing other treatments as a first line option for the treatment of PD. This would not only be very cost-effective (for patients and the overall healthcare system), it would also provide a less-invasive option for treatment with fewer long-term risks. It therefore has the possibility of changing the entire paradigm for managing the condition of PD.

## 4 STUDY DESIGN AND METHODS

#### 4.1 Subject Selection

- 4.1.1 Inclusion Criteria
  - Males with previously diagnosed PD
  - >18 years old

#### 4.1.2 Exclusion Criteria

- Prisoners
- Curvatures <30 degrees
- Stretched penile length <7 cm

- Currently undergoing intralesional injections for PD
- Erectile dysfunction (ED) unresponsive to phosphodiesterase-5 inhibitors or intracavernosal injection therapies
- Diabetes mellitus with evidence of end-organ damage (peripheral neuropathy, retinopathy, CKD stage III or higher, etc.)

## 4.1.3 Setting

The current study will be conducted at the Mayo Clinic in Rochester, MN on Gonda 7 South (Dept of Urology). All patients will be recruited from [name] clinical practice, as [name] is the only Andrologist treating men with PD at Mayo Clinic Rochester. All aspects of recruitment, education, and objective assessments will occur within [name] practice.

#### 4.1.4 Recruitment and Pre-Screening

Recruitment will occur from patients treated at Mayo Clinic for Peyronie's disease. Contact will occur via mailers and provider-initiated telephone calls after assuring that the patients meet the appropriate inclusion / exclusion criteria. Patients who would be interested in proceeding with the trial will be invited to an introductory meeting, at which time details of the study itself would be reviewed. No financial incentives will be provided to participate in the trial, however, participants would be given a RestoreX® device at no charge. Patients will not be charged for any visits related to the study, and no labs or other testing will be obtained which require payment.

Patients indicating that they would wish to participate will be reviewed to again assure that they meet the appropriate inclusion and exclusion criteria.

#### 4.1.5 Consent and Enrollment

Following initial recruitment, patients will be scheduled for an introductory and orientation appointment. Specific study details and requirements will be reviewed at that time, and if the patients express interest in participating, a formal consent will be reviewed.

If the patient successfully completes the consenting process, they will undergo initial assessments as described later in the protocol. At enrollment, all patients will be assigned a study identifier, with a master list maintained in a password protected database (Mayo server) linking the patient to the identifier. A goal of 25 patients will be enrolled into each arm of the study, with an estimated 120 enrolled to achieve this number (due to anticipated dropouts, failure to comply). It is estimated that 250 patients will need to be screened to enroll the 120 patients.

## 4.2 Study Schema

Once patients have agreed to receive further information on the study, an initial consult will be established. Patients who are currently taking other therapies for PD will be requested to stop these therapies for a minimum of 4 weeks prior to the appointment to assure an adequate washout period prior to being enrolled.

During the initial appointment, the patient will receive a description of the study, initial education on how to use the device properly, and informed consent. Those consenting to the procedure will

receive initial study assessments (see below). Those wishing additional time to consider enrollment may be rescheduled to a later date if desired. Once consent is completed, the patients will be randomized into one of four groups: PTT 30 min 1x/day, 30 min 2x/day, 30 min 3x/day, or control (no treatment).

Patients will then begin using the devices as previously instructed for the times appropriate to their group. After 3 months (+1.5 months permitted), patients will return for subsequent assessments (see below). After completion of the subsequent assessments, patients will begin a 3-month, open-label phase of the trial. During this period, the patients will be allowed to use the device for 30 minutes at a time, with a frequency to be determined by the patient.

After completion of the open-phase portion of the trial, patients will undergo final assessments, which are identical to the 3-month assessments. Patients will then be encouraged to self-report any additional adverse events (AE's) that they encounter over the subsequent 3 months after discontinuing the therapy and will be contacted by telephone for a final question / adverse event assessment (9 months after study initiation).

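### The 4-week washout of other Peyronie's therapies is requested before the appointment at which the protocol takes informed consent

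*Combined protocol and SAP*

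**What the plan says.** Section 4.1.4 (Recruitment and Pre-Screening) has the practice contact its own patients by mail or telephone "after assuring that the patients meet the appropriate inclusion / exclusion criteria". Men who show interest at that stage "will be invited to an introductory meeting, at which time details of the study itself would be reviewed". A second eligibility review follows for those who say they wish to take part.

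Section 4.1.5 (Consent and Enrollment) has study details reviewed at an introductory and orientation appointment, and "if the patients express interest in participating, a formal consent will be reviewed". It then says: "If the patient successfully completes the consenting process, they will undergo initial assessments as described later in the protocol".

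Section 4.2 (Study Schema) begins: "Once patients have agreed to receive further information on the study, an initial consult will be established". Men on other Peyronie's therapies "will be requested to stop these therapies for a minimum of 4 weeks prior to the appointment", so that they are adequately washed out by enrolment. The study description, device education and informed consent are all assigned to the initial appointment. A man who wants more time to decide may be rebooked. After consent, men are randomized to one of three traction schedules or to no treatment.

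**The concern.** A washout done for the study is a study procedure, because it changes what a man does about his condition for the sake of the research. Consent normally comes first. Here the only agreement recorded before the stop request is interest in the trial or willingness to hear more about it.

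At stake is the position of men on other therapy. Some will attend and decline, some will defer, and some will be found ineligible when measured. They will have interrupted treatment without documented consent and with no place in the trial in return. Those who enrol will also have paused before consenting. A man may stop before the formal review of the fact that one arm in four receives no treatment.

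**Working it through.** The protocol gives no figure to reproduce for this point. The check is one of sequence, reading Sections 4.1.4, 4.1.5, 4.2 and 4.2.1 together.

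1. **Contact** (4.1.4): mailer or telephone call, after a first eligibility check. No consent step is described.
2. **Agreement before the visit** (4.1.4, 4.2): interest in proceeding, or agreement to receive further information.
3. **Stop request** (4.2): at least 4 weeks before the appointment, that is 4 × 7 = 28 days or more. The purpose given is washout; no clinical reason is offered.
4. **Appointment** (4.1.5, 4.2): study description and informed consent.
5. **Baseline measurement** (4.1.5, 4.2.1): after consent and before randomization.
6. **Randomization** (4.2, 4.2.3): one of four groups, so 1/4 = 25% are allocated to no treatment.

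The pause at step 3 precedes consent at step 4. No interval is described between steps 4 and 5 into which a washout could fit, so the order does not look like a slip of wording.

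**Does the conclusion depend on how the visits are labelled?** The three sections use different names: introductory meeting (4.1.4), introductory and orientation appointment (4.1.5), and initial consult or appointment (4.2). The likeliest reading is a single visit, since 4.1.5 and 4.2 both put consent there. If the meeting in 4.1.4 were a separate, earlier visit, study details could have been reviewed before the washout. Section 4.2 would still place consent at the appointment that the washout precedes.

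**Can a man fail eligibility after pausing?** Section 4.1.2 excludes curvature below 30 degrees and stretched length below 7 cm. The study's own measurements of both come at step 5, so failure there remains possible despite the checks in 4.1.4. No rate is given.

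**Who is exposed?** Section 3 lists oral, intralesional, and mechanical vacuum or traction therapies as the non-surgical options. Section 4.1.2 excludes men currently having intralesional injections. The request therefore mainly concerns oral, vacuum or other traction therapy. The share of candidates using these is not stated.

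**The case against.** The strongest objection is that the gap may be closed in material that is not visible. Consent pages are not in the review copy, and the mailers and call content are not reproduced. An approved screening consent or waiver could sit there. That stands as a limit on the conclusion. A reader might infer that the trial changes treatment with no consent or ethics approval of any kind, and the documents do not support that. They support only that the protocol body sets this order and cites nothing that covers it.

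Second, the step is a request to men who have already shown interest, made after an eligibility check before contact, with another once a man wishes to take part. Section 4.1.4 does not date that second check relative to the washout. These points lower the risk. They do not supply consent, and they do not rule out failure at the baseline measurement.

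Third, men may already have been told about the no-treatment arm. A reader might infer that they pause in ignorance of it, but what the mailers and calls say is unknown. It can be said only that the formal review of study details is placed at the appointment.

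Fourth, a reader might try to size the problem from 4.1.5: "It is estimated that 250 patients will need to be screened to enroll the 120 patients". The difference, 250 - 120 = 130, is not a bound. The pause also affects men who enrol, including those who first defer; only men on other therapy are concerned; and the term screened is undefined. The documents support no count.

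**Conclusion.** The point holds as a matter of stated order: a research washout of at least 28 days is requested before the appointment at which consent is placed. It applies to any man on other therapy who complies, whatever he later decides. The conclusion assumes that the appointment in the washout sentence is the consent appointment, which is how 4.2 reads, and that no approved screening consent or waiver already covers the pause.

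Severity is low. The number of men affected cannot be estimated, the documents show no harm from the pause, and no endpoint, estimate or power figure changes. A reader might infer that the trial's results are compromised; nothing here supports that, since the washout itself is reasonable and only its timing relative to consent is at issue. It is worth changing because the remedy is cheap and keeps the washout intact.

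**What to change.** Amend 4.1.5 and 4.2 so that one of the following comes before any study-driven request to stop therapy:

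- full informed consent; or
- an IRB-approved screening consent, possibly remote, that covers the washout and the possibility of allocation to no treatment.

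For men on other therapy, set baseline assessment and randomization at least 4 weeks after stopping. If an approved screening consent or waiver already covers the washout, cite it in 4.2.

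The cost is protocol wording and one extra contact for men on other therapy; men on none are unaffected. Some men will now consent and then fail the curvature or length limits. They should be recorded as screen failures and kept out of the 120. The target is 4 × 25 = 100 evaluable men, so 120 leaves 120 - 100 = 20 for dropout and non-compliance, and screen failures should not use up that margin. Section 4.1.5 should say at which step a man counts as enrolled.

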#### 4.3.3 Statistical Analysis

All data will be entered into JMP Pro 10.0.0 (SAS Institute, Cary, NC). Differences between groupings will be analyzed using tests appropriate to the specific conditions: Wilcoxon, matchedpairs, student's t-test, ANOVA, ANCOVA, chi-squared, or Fisher's tests. All relevant tests will be 2-sided, with a p-value of <0.05 defined as significant. Differences in AE's will be determined based on total number of reported events as well as individual assessments of each individual event.

During the first phase of the study, results will be analyzed as a whole to determine the percentage of men who were non-compliant (both in methods of utilizing the device and percentage of time spent using the device) or dropped out. These data will determine the ability of men to utilize the device as recommended. Data will be analyzed both with and without these non-compliant / dropout men included. Non-compliance will be determined by failure to bury the white indicator line regularly with straight stretch, failure to achieve 90 degree bending during majority of uses, and failure to perform traction for at least 90% of days recommended.

Analyses will be performed using comparisons within patients (changes from baseline to 3 months, from 3 months to 6 months, from baseline to 6 months) and between groupings. ANCOVA will be used (adjusting for baseline values of curvature direction, curvature degree, and baseline penile length). Additional analyses will be performed to analyze the impact of prior treatments (such as intralesional injections) on outcomes. The use of ANCOVA is anticipated to increase the effect size slightly to 0.302 (assuming R^2 value of 0.2 for curvature direction, curvature degree, and baseline penile length).

Assessments will also be performed comparing any degree of traction (i.e. groups 2-4) against no traction. Additional assessment will also be performed based on the total duration of traction applied (time per day multiplied by number of days used) to assess for differences in outcome variables.

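### Compliance in 4.3.3 is judged by days with traction, not sessions or minutes, so off-schedule use in either direction passes as compliant although the device arms differ only in sessions per day

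*Combined protocol and SAP*

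**What the plan says.** Section 4.2 (Study Schema) sets four groups: "PTT 30 min 1x/day, 30 min 2x/day, 30 min 3x/day, or control (no treatment"). Between the three device arms, sessions per day is the only difference. Men are then told to keep to their group's schedule: "Patients will then begin using the devices as previously instructed for the times appropriate to their group". After the 3-month visit all men enter an open-label phase, "with a frequency to be determined by the patient".

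The sole primary objective (2.1) is tied to these schedules: "Evaluate the safety of the RestoreX® device when used 30 minutes once daily, twice daily, three times daily, and in an open label fashion".

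Section 4.3.3 makes non-compliance operational through three failures:

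- "Non-compliance will be determined by failure to bury the white indicator line regularly with straight stretch" (technique)
- "failure to achieve 90 degree bending during majority of uses" (technique)
- "failure to perform traction for at least 90% of days recommended" (usage)

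The results are to be analysed once with and once without the non-compliant men and dropouts. The same section plans a further assessment by total traction time, the product of daily time and days of use.

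**The concern.** The randomised contrast between device arms is a contrast in sessions per day, but no compliance criterion looks at sessions or minutes per day. The two technique criteria concern how the device is applied. The usage criterion concerns on how many days it is applied. A man can therefore be far from his assigned schedule, above or below it, and still be classed as compliant.

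Two results are exposed. First, the analysis without non-compliant men is likely to be read as showing each schedule as actually followed, and the rule cannot deliver that. Second, the by-schedule safety result, which is the primary objective, labels events by assigned schedule. Events arising at 90 min/day could be reported under 30 min/day, and the reverse. Off-schedule use towards the other arms makes the schedules look more alike than they are, for harm and for effect. The rule also does not address a control man who uses a device before the 3-month visit, although 6.2 says the device can be bought without a prescription.

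**Working it through.** **1. The rule applied to individual men.** Inputs: 30-minute sessions, one to three a day (4.2), and the 90% day threshold (4.3.3). A 3-month phase is taken as 90 days (assumption), and technique as acceptable. Assigned minutes = 30 × sessions × 90.

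| Man | Assigned min | Actual use | Achieved min | Share of assigned | Day criterion |
|---|---|---|---|---|---|
| 1x/day | 30 × 1 × 90 = 2,700 | 3 sessions on 90 days | 8,100 | 300% | passes |
| 3x/day | 30 × 3 × 90 = 8,100 | 1 session on 90 days | 2,700 | 33% | passes |
| 3x/day | 8,100 | 1 session on 81 days (90%) | 2,430 | 30% | passes |

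The first man has the full exposure of the 3x/day arm. The second has the full exposure of the 1x/day arm. Both stay in their assigned arm in both planned analyses.

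**2. The plan's own power figure.** Section 4.3.2 gives an effect size of 0.3370 for four arms of 25 at 80% power and 0.05 significance. With the noncentral F distribution (df 3 and 96, noncentrality 100 × f²), f = 0.33699 gives 80% power. The stated figure is reproduced and this point does not alter it.

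**3. Illustration of blurring.** Assumptions, none from the documents: the effect is linear in minutes per day; it is scaled so that 0, 30, 60 and 90 min/day give f = 0.337; and a share c of men drift, either 1x and 2x men up to 3x, or 2x and 3x men down to 1x. The extra within-arm spread is ignored.

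The standard deviation of the four means is 33.54 min, so one outcome SD corresponds to 33.54 / 0.337 = 99.5 min. The 3x-minus-1x separation is 60(1 − c) min/day in either direction of drift, and the standardised difference is 60(1 − c) / 99.5, which is 0.603 at c = 0.

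| c | 3x − 1x, min/day | Power, 3x vs 1x | Power, three device arms | Power, four arms, drift up | Power, four arms, drift down |
|---|---|---|---|---|---|
| 0 | 60 | 57% | 45% | 80% | 80% |
| 10% | 54 | 48% | 37% | 79% | 73% |
| 20% | 48 | 40% | 30% | 79% | 66% |
| 30% | 42 | 32% | 24% | 80% | 58% |

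The 3x-vs-1x column uses a normal approximation with 25 per arm; a t-test gives 55%, 47%, 39% and 31%. Over-use leaves the overall test with control almost unchanged and affects only comparisons between schedules. Under-use weakens both.

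**4. Illustration for adverse events.** Assume true risks of 10% at 1x and 25% at 3x. If a share u of 1x men use the device 3x, that arm shows 0.10(1 − u) + 0.25u = 11.5%, 13.0% or 14.5% at u = 10, 20 or 30%. If a share u of 3x men use it 1x, that arm shows 0.25(1 − u) + 0.10u = 23.5%, 22.0% or 20.5%. In men out of 25, the 1x arm moves from 2.5 to between 2.9 and 3.6. Even with no drift, Fisher's exact test of 10% vs 25% with 25 per arm has only 18% power.

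**The case against.** **The total-duration assessment already uses achieved minutes.** This stands in part. It places each man by actual use and implies that daily time is collected. But it is a non-randomised, additional look at outcome variables that does not name adverse events, and it changes neither the compliance class nor the by-schedule results. The planned review of individual events does not change them either.

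**The criterion could be read as days on which the full assigned schedule was done**, since the section also speaks generally of the percentage of time the device was used. The operative sentence does not say so, and on that reading there would still be no upper limit.

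**The analysis of all men as randomised is unaffected.** True. Off-schedule use is part of the effect of assignment there, and that analysis should be kept.

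**Excluding off-schedule men is selection after randomisation.** This stands. 1x men have more room to exceed their schedule and 3x men more room to fall short, so exclusions may differ by arm.

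**Over-use is not documented.** This also stands. A reader might infer that the rule catches under-use and misses only over-use, or that over-use is to be expected because men hold the device, know their arm and later choose their own frequency. The documents support neither inference. The day count also misses too few sessions. Men are told to follow their schedule, and free choice starts only after the 3-month visit. The one remark on achieved use (3.1, about an existing device) says most men cannot exceed 1–2 hours daily, which points towards under-use.

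**Conclusion.** The concern holds in two directions. The usage criterion in 4.3.3 does not measure the quantity that separates the device arms, so the analysis without non-compliant men does not remove off-schedule use above or below assignment, and schedule-specific safety and efficacy comparisons can be blurred. That follows from the text and needs no assumption about behaviour.

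The size is unknown because the documents give no rate of over- or under-use. The power and event figures above are illustrations that rest on assumed drift to the extreme schedule, a linear effect and assumed risks. The 3x-vs-1x contrast is also not one that 4.3.2 powered. It would go too far to conclude that the by-schedule results are invalid or that the trial's stated power is wrong: the power figure reproduces, and the as-randomised comparison remains sound as an effect of assignment. This is a defect in a definition, worth correcting because it bears on the primary objective and is cheap to mend.

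**What to change.** In 4.3.3, define usage compliance for analysis against the assigned schedule in both directions. One form is achieved sessions or minutes as a percentage of those assigned, with a stated lower and upper limit. In control, count any device use before the 3-month visit. The technique criteria can stay as they are. Then:

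- report under-use and over-use separately by arm;
- apply both limits in the analysis without non-compliant men, and label it supportive;
- keep all men as randomised in the other analysis and name it the main comparison;
- tabulate adverse events by achieved use as well as by assigned schedule.

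This classifies data for analysis only and changes no treatment schedule.

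Cost: a few sentences in 4.3.3 and added columns in the compliance and adverse-event tables. The daily time needed for the total-duration assessment should serve, but the usage forms are not visible in the documents. An average daily time would support a percentage-of-assigned measure; linking an event to use at that moment would need dated records. Fewer men will remain in the supportive analysis, and the exclusions may be uneven across arms, which is why it should not carry the main conclusion.
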